3. SUBJECTS

a. Description of Study Populations

- Participants will be 18 to 50 years old and will be diagnosed with one of the following: generalized anxiety disorder, panic disorder, SAD, specific phobias, major depression, and bipolar depression according to DSM-IV. Patients on scheduled/regular psychotropic medications, other than lithium or Depakote, will stay on their medication. Although patients will not be taken off medications for the purposes of this study, included patients will not be currently taking psychiatric medications or any other medications that may interfere with study results (see exclusion criteria for other characteristics of patient sample). The only

exception is that bipolar depressed patients may be taking mood stabilizers, either lithium carbonate or Depakote. Subjects taking PRN medication that is allowed according to the medication table below, must be both willing and safely able to hold the medication for 5 half-lives. Additionally, healthy controls who are age and sex matched to patients will be studied.

- The accrual ceiling is 608 patients with mood or anxiety disorders and 663 healthy volunteers. This accrual ceiling includes a drop out/withdrawal/non-analyzable data rate of 15% for sub-studies 1 (11 patients, 44 controls) and 2 (115 patients, 86 controls) and 25% for sub-study 3 (38 patients, 38 controls).
- NIH, but not NIMH, employees may participate. NIH employee participation is guided by intramural institute policy.

b. Inclusion criteria for both patients and healthy controls

- All subjects must be able to give written informed consent prior to participation in this study.
- PATIENTS ONLY: May have DSM-IV-TR diagnoses of an anxiety disorder (GAD; SAD; Panic disorder; specific phobia) or mood disorder (MDD; BP).
- PATIENTS ONLY: May be taking the mood stabilizers, Depakote or Lithium Carbonate.
- Speaks English fluently
-

c. Exclusion criteria for healthy subjects

- Female subjects who are currently pregnant
- Subjects who meet DSM-IV criteria for current alcohol or substance abuse
- Subjects with a history of alcohol or substance dependence within 6 months prior to screening
- Current Axis I psychiatric disorders as identified with the Structured Clinical Interview for DSM-IV-TR axis disorders, non-patient edition (SCID-np). Past history of any psychotic disorder or bipolar disorder.
- IQ < 80

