10. STASTISTICAL ANALYSIS

The overall target N for the protocol is 663 healthy controls and 608 patients. Participants who drop out will be replaced. Participants may participate in more than one sub-study.

- Sub-study 1
 - **Analysis of data/study outcomes:** Startle amplitude during the verbal threat procedure will be averaged over cue and no cue (ITI) periods within conditions. There will be separate analyses for anxiety disorders and mood disorders. The data will be submitted to a Group (GAD, SAD, panic disorder, control or MDD, bipolar, control) x Condition (P, N, U) x Cue (cue, ITI) ANOVA. If this interaction is significant, within-group simple-effects comparing startle amplitudes during the ITI of predictable versus unpredictable conditions will be compared for all groups separately. Larger startle magnitudes in the unpredictable versus predictable condition suggest heightened sensitivity to unpredictability. Between group contrasts will also be computed to compare difference scores (i.e., differences between startle magnitudes during unpredictable and predictable conditions) across groups. In our pilot and published studies, we obtained the lowest effect size ($f=0.30$) for contextual fear (anxiety-potentiated startle).

- **Power analysis:** We set power at .80 and experiment-wise, two-tailed alpha at 0.05. Based on these parameters, we will need 18 subjects per group. Assuming a 15 % unusable data rate due to lack of startle response or equipment failure, approximately 22 subjects per group will be recruited for a total of 110 patients and 44 healthy controls.
- Sub-study 2
 - **Analysis of data/study outcomes:** Startle amplitude will be averaged over conditions (safe, threat) and WM load (View, 1, 2, 3). There will be separate analyses for anxiety disorders and mood disorders. The data will be submitted to a Group (GAD, SAD, panic, controls or MDD, bipolar, controls) x condition (safe, threat) x WM load (1-back, 2-back, 3-back).

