 - **Power analysis:** Based on our published study in healthy controls (Vytal et al, in press), where we found a 2-way interaction between condition and WM load with an effect size of $\eta^2=0.20$, we estimate that we will need 20 subjects per group. Given a rate of 15% of unusable data, approximately 23 subjects per group will be recruited for a total of approximately 115 patients and 46 healthy controls. We will also need approximately 40 healthy controls to pilot various versions of the tasks for a total of 86 controls.
- Sub-study 3
 - **Analysis of data/study outcomes:** patients will be tested twice, before and after the 8-week treatment, while controls will be also tested twice, 8 weeks apart. Startle amplitude and performance will be averaged over conditions (safe, threat) and WM load (view, 1, 2, 3 for startle and 1, 2, 3 for performance). These data will be submitted to omnibus Group (patients, controls) x condition (safe, threat) x WM load (view, 1-back, 2-back, 3-back for startle and 1-back, 2-back, 3-back for performance) x Time (first session, second session) ANOVAs. However, the analysis will focus on the 3-back condition, where greater group differences are expected. Changes in fear-potentiated startle and differential performance (threat minus safe) in the 3-back condition from session 1 to session 2 will be compared between the two groups. Secondary measures will be subjected to multiple-regression analyses. For all such analyses, questionnaire scores will serve as predictor variables and different experimental outcomes will serve as dependent variables. Analyses will regress questionnaire scores dependent measures of interest: 1) anxiety-potentiated scores, 2) WM scores, and 3) attentional-bias scores. In so doing, we will be able to assess the combined and unique contributions of questionnaire scores to the variability in dependent measures.
 - **Power analysis:** We estimate that we will need 30 subjects per group. Given a rate of 25% of unusable data or non-completers, approximately 38 controls and 38 patients will be recruited.

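### Sub-study 2 recruits about 23 per group for a need of 20 at 15% loss; at that rate 23 gives an expected 19.55 usable, and Sub-study 1 inflates by a different rule

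*Combined protocol and SAP*

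**What the plan says.** Section 10, Sub-study 2, Power analysis, gives the requirement: "we estimate that we will need 20 subjects per group". It then allows for loss: "Given a rate of 15% of unusable data, approximately 23 subjects per group will be recruited", and scales up: "for a total of approximately 115 patients and 46 healthy controls". Forty pilot controls bring the controls to 86. No formula is shown for the step from 20 to 23.

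Two other passages in the same section allow for loss. Sub-study 1 needs 18 per group at 15% unusable data, and "approximately 22 subjects per group will be recruited". Sub-study 3 needs 30 per group at 25% loss, and "approximately 38 controls and 38 patients will be recruited". Section 4a says Sub-study 3 is stopped.

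Two statements bear on what the 15% covers. Section 3a pools several kinds of loss: "This accrual ceiling includes a drop out/withdrawal/non-analyzable data rate of 15% for sub-studies 1" (the sentence goes on to include Sub-study 2). The opening of Section 10 gives one replacement rule: "Participants who drop out will be replaced". It does not mention participants who stay but whose data cannot be used.

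**The concern.** To end with n usable subjects when a fraction d is lost, the number recruited must be n/(1 - d). Multiplying by (1 + d) always falls short, because the loss applies to the larger recruited number. The 23 in Sub-study 2 equals 20 x 1.15 exactly, so it looks like the multiplying version.

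What is at stake is modest. A reader who applies the stated 15% to the stated 23 does not get back the stated 20, and two active sub-studies with the same loss rate are inflated differently. The figure also recurs: 115, 46 and 86 are built on 23, and at least some of them appear in the front-page accrual list, Section 3a, Section 4d and Section 10.

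**Working it through.** **Inputs (Section 10).** Sub-study 2: need 20, loss 15%, recruited 23. Sub-study 1: need 18, loss 15%, recruited 22. Sub-study 3: need 30, loss 25%, recruited 38. Sub-study 2 has five patient groups (GAD, SAD, panic, MDD, bipolar) and, from the totals, two control sets, so seven groups.

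**The plan's totals reproduce.** 5 x 23 = 115 patients; 2 x 23 = 46 controls; 46 + 40 pilots = 86 controls; 115 + 46 = 161 before pilots.

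**Which rule gives the recruited numbers?**

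| Sub-study | Need | Loss | Need x (1 + loss) | Need / (1 - loss) | Plan |
|---|---|---|---|---|---|
| 1 | 18 | 15% | 20.7, up to 21 | 21.18, up to 22 | 22 |
| 2 | 20 | 15% | 23.0 | 23.53, up to 24 | 23 |
| 3 (stopped) | 30 | 25% | 37.5, up to 38 | 40.0 | 38 |

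Sub-study 1 fits division rounded up. Sub-study 2 fits multiplication exactly, but would also fit division rounded down. Sub-study 3 fits multiplication only: 30/0.75 is exactly 40, so no rounding of a division gives 38. Division rounded down would give 21 in Sub-study 1, not 22. No single rule reproduces all three numbers.

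**Expected usable at the plan's own loss rate.**
- Sub-study 1: 22 x 0.85 = 18.7, which meets 18.
- Sub-study 2: 23 x 0.85 = 19.55, which is 0.45 below 20. Over seven groups: 161 x 0.85 = 136.85 against 140, or 3.15 short.
- Sub-study 3: 38 x 0.75 = 28.5 against 30.

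**Break-even loss for 23 recruited.** 1 - 20/23 = 13.0%. The plan states 15%.

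**With 24 per group.** 24 x 0.85 = 20.4 expected usable. Totals: 5 x 24 = 120 patients; 2 x 24 = 48 controls; 48 + 40 = 88 controls with pilots; 120 + 48 = 168 against 161 before pilots.

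**Room under the ceiling.** The sub-studies on the front page sum to 110 + 115 + 38 + 30 + 30 + 30 + 40 = 393 patients and 44 + 86 + 38 + 30 + 30 + 40 = 268 controls, against ceilings of 608 and 663. With 24 per group the sums become 398 and 270.

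**The case against.** The best defence is that the plan is deliberately approximate. It estimates the 20 and marks the 23 and the totals as approximate, and 15% is a planning guess; an expected 19.55 rounds to 20. This stands as a limit on size. It does not remove the mismatch, because the approximate 23 is carried forward as exact multiples (115 and 46).

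Second, multiplication is inferred. The plan shows no formula, and 23.53 rounded down is also 23. That is fair, so the cause should be put as consistent with multiplying. Sub-study 3 supports the inference, but only as evidence, since that sub-study is stopped. Whatever the cause, 23 at 15% loss does not give 20 in expectation.

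Third, drop-outs are replaced, and Section 3a counts drop-outs within the 15%. If each replacement is usable with probability 0.85, closing the gap takes 0.45/0.85 = 0.53 replacements per group, roughly one for every two groups. Replacement could therefore cover it. However, the plan does not split the 15% between drop-outs and unusable records, and the rule as written covers only drop-outs. Sub-study 1 describes its unusable data as absent startle responses or equipment failure, which arise in people who attended. The protection is partial.

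A reader might also infer three stronger things that the documents do not support:
- **That power is lost.** The Sub-study 2 paragraph gives an effect size but no alpha, power or formula, so there is no stated power against which a loss could be shown.
- **That the accrual ceiling is wrong.** Five more patients and two more controls leave the listed sub-studies well below 608 and 663.
- **That the groups will almost certainly miss their target.** With independent losses and no replacement, the chance of at least 20 usable from 23 is 0.54, or about 1% for all seven groups together (0.54 to the seventh power). The plan sets no such joint criterion and does replace drop-outs. The same calculation at 24 gives 0.71 per group and about 9% for all seven. It mainly measures chance variation around an expected value, not the inflation step.

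**Conclusion.** The point holds as a minor consistency correction. At the stated 15%, about 23 recruited per group gives an expected 19.55 usable against a stated need of 20. The number is consistent with multiplying where division gives 24, and Sub-study 1 follows the division rule at the same rate. The size is 0.45 of a usable subject, or one recruit, per group.

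This rests on taking 15% as the loss among those recruited, 20 as the usable number required, and the replacement rule as limited to drop-outs, which is how the text reads. The 20 itself was not checked: it is drawn from a within-subject condition by memory-load interaction in healthy controls, and the paragraph does not give enough to rebuild it.

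**What to change.** Make one of these edits to the Sub-study 2 power paragraph in Section 10:

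1. **Restate the yield.** Keep 23 and say that it gives an expected 19.55 usable subjects per group at 15% loss. No total changes; the stated usable size becomes slightly less favourable.
2. **Make 20 usable the target.** Keep 23 as the initial recruitment and extend the replacement rule at the head of Section 10 to participants with unusable data. This takes one sentence and is the sturdier choice, because it also covers chance variation in losses.
3. **Correct the recruitment figure.** Use 24 per group: 120 patients, 48 controls, and 88 controls with pilots. Update the totals on the front page, in Section 3a, in the Sub-study 2 text of Section 4d, and in Section 10. The cost is five more patients and two more controls.

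Showing the formula next to the number in Sub-studies 1 and 2 would prevent the question from recurring. Sub-study 3 is stopped, so changing its figure would alter nothing going forward.

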11. HUMAN SUBJECT PROTECTIONS

a. *Subject selection*

i. Statement of equitability:

- The race distribution of the samples studied in this project will be similar to that of the greater Washington DC metropolitan area, and will include representation from all minorities excepting American Indians, who we have much less opportunity to study. Because the NIMH is located in a suburban area in which African-Americans may be under-represented, if at any point the race composition of subjects recruited during the proposed imaging study fails to reflect the race distribution of the larger geographic area, we will intentionally emphasize recruitment of subjects from more urban areas through collaborations being formed with Howard University. While we have not found significant race effects on the clinical or psychobiological parameters assessed, we will continue to perform secondary analyses to explore potential effects of race on these domains.
- We exclude non-English speakers since not all the instruments and test we use are translated and validated in Spanish or other languages.
- We expect ***to enter about equal number of females*** and males in the study. Pregnant females will be excluded because the effects of shock are unknown on a developing fetus. The upper limit for age range of 50 years is set to achieve greater homogeneity in our sample and thereby reduce the variability of the startle reflex, which tend to decrease with increased in age. This is necessary to increase the signal to noise ratio and the sensitivity of our study to detect differences between conditions.

ii. Rationale for selection if not equitable

N/A

b. Justification for inclusion/ exclusion of children

- In order to elicit anxiety responses similar to those occurring in anxiety disorders it is important that out stressor is highly unpleasant. We thus chose to use electric shock as the stressor. Though shock stressors are well tolerated by adults (and used frequently in the literature to assess stress reactions in healthy and disordered individuals), such methods may be inappropriate for children. We will not enter children under age 18 because of ethical concerns about exposing them to threat of shock. Moreover, concerns regarding the legal inability to provide informed consent before age 18 (and the consequent dependence on parental decision) preclude inclusion of subjects under age 18.

c. Justification for inclusion of other vulnerable subjects, e.g. cognitively impaired, pregnant, mentally ill

We exclude patients with cognitive impairment as they would be unable to self-administer the necessary test instruments. Subjects with other Axis I disorders other than mood and anxiety

disorders because of the confounding effects of other psychiatric disorders. Pregnant women are excluded because the effects of MRI and shocks on the fetus are not known.

- d. Justification of sensitive procedures (use of placebo, medication withdrawal, provocative testing)*
 - Electric shocks are used as the stressor in this study. Our use of electric shocks stems from our experience that electric shocks are among the most efficient ways to induce anxiety in the laboratory setting and to detect patients control differences.
- e. Safeguards for vulnerable populations e.g. DPA, pregnancy testing, contraception use, ethics consult, HSPU involvement*
 - We assess pregnancy via urine test within 24 hours of any testing and exclude all participants who are pregnant.
 - Protections for NIH employees, staff and family members participating in this study include 1) assuring that the participation or refusal to participate will have no effect, either beneficial or adverse, on the subject's employment or position at the NIH, 2) giving employees and staff who are interested in participating the "NIH Information Sheet on Employee Research Participation" prior to obtaining consent, and 3) assuring that there will be no direct solicitation of employees or staff. This study collects sensitive information (e.g. drug and alcohol use, specific medical diagnoses). The PI will train study staff regarding obtaining and handling potentially sensitive and private information about NIH employees, staff and family members through staff discussions and written branch/section procedures. Prior to enrollment, potential participants will be informed that sensitive information (e.g. drug and alcohol use, specific medical diagnoses) will be in the participant's NIH medical record.

12. ANTICIPATED BENEFIT

- The experimental procedures involved in this study provide no direct benefit but are likely to yield generalizable knowledge about the psychophysiology of anxiety in health and disorder. Results from this study may help others with similar diagnoses in the future by facilitating the development of more effective assessment and intervention strategies for anxiety disorders.

14. CONSENT DOCUMENTS AND PROCESS

- a. Designation of those obtaining consent
 - Study investigators designated as able to obtain consent listed in KSP form, will obtain informed consent. Consent for NIH employees, staff and family members will not be obtained by coworkers.
- b. Consent procedures
 - All participants will receive a verbal explanation in terms suited to their comprehension of the purposes, procedures and potential risks of the study and of their rights as research participants. Participants will have the opportunity to carefully review the written consent form and ask questions regarding this study prior to signing.
 - Prior to commencement of the experiments, all participants will have been fully informed and will be consented under protocol 03-M-0093. There will be two separate consents, one for controls, and one for anxiety volunteers.
 - Telehealth Consent Procedures: Under certain circumstances, there may be a need to obtain telephone or telehealth consent for this study using NIH-approved platforms. Under these circumstances, the individual will be sent a copy of the consent form. After the document is reviewed, an AI authorized to obtain consent will contact the individual and review the procedures and risks. The participant and the investigator will sign their respective copies, and the former will return their copy to the investigator. One copy each of the signed consent form will be placed in the Medical Record, retained by the investigator, and returned to the participant or parent/guardian. Proper documentation will be made in CRIS.
 - Informed consent for the study will be obtained in-person or via Telehealth prior to any tests. The consent forms include a checklist that includes all procedures outlined in the protocol. Prior to consenting, all procedures subjects will experience will be marked so that the participant understands exactly what they will be doing. If a subject returns to do a different task within the same protocol, they will be re-consented with appropriate procedures marked
 - During the consent process, participants will be reminded that their participation is voluntary and that they may discontinue their participation at any time without jeopardizing their continuing medical care at this institution, or losing benefits they would otherwise be entitled to. Patients will be informed that they will be provided with treatment recommendations, short-term treatment, and referrals to other treatment providers should they decide to withdraw from the study. All subjects will also be informed that Drs. [name] or [name], or other psychiatrists acting for them, will have the right to withdraw them from the study at any time for clinical reasons or if they have failed to follow instructions. Importantly, patients will be informed that upon completion of the study they will be provided with continued short-term treatment for their psychiatric disorder at no cost at the NIH for up to two months after which they will be referred to an appropriate psychiatric team for long-term treatment.

- All subjects who will participate in studies 1 and 2 (that do not involve CBT) will be informed that no immediate personal medical or psychiatric benefits will be derived from participation. It will be explained that these experiments are designed to gain information that will lead to better understandings of the associations between brain function and anxiety arousal that will potentially benefit individuals with anxiety disorders in the future, but that the results will not be helpful for indicating current treatment, diagnosis, or prognosis.
- Subjects will be informed of all potential risks of participation during the consenting process. Of note, patients with anxiety and/or mood disorders will be told that the study is not designed to treat their psychiatric disorder/s and that their condition may worsen while participating in this study.
- Additionally, patients participating in studies 1 and 2 will be reminded that psychopharmacologic and psychotherapeutic treatment options for anxiety and mood disorders are available in clinical practice outside of the NIH and delaying such treatment may have adverse effects on their mental health. During the consent process, anxiety patients will be told that [name] will be assigned to them as their primary psychiatrist should they participate in the study and that they will be given [name] pager number as well as other methods for contacting NIMH psychiatrists 24 hours a day, 7 days a week. The same procedure applies to depressed patients, who will be provided with [name] contact information.

c. Consent documents

- All consent forms include the required elements
- Consent documents submitted with this protocol include: Control, Patient, and Cognition

